2.4.8. ENGAGEMENT

The proportion of participants in the tCBT treatment arm who attended the initial assessment, 0 to 6 weekly sessions, and the booster sessions at 3 and 6 months will be tabulated. The proportion of participants completing treatment (there is mutual agreement between therapist and participant to stop treatment AND at least one session (the initial assessment) has been attended; OR, participant has at least 3 sessions of CBT (including the initial assessment)) will also be tabulated.

2.4.9. RESPONDER ANALYSIS

Within the treatment group, those participants in the treatment group who do not have the outcome chronic widespread pain (CWP) at 12 months will be compared with those in the treatment group who do have (CWP) in terms of other variables. The other variables will be the three risk variables: symptoms, illness behaviour and sleep problems; and in addition: age; gender; health board; distress from General Health Questionnaire; fatigue; QoL from EQ5D; QoL from ICECAP; completion of treatment; and length of time between randomisation and treatment start.

Simple comparisons between those within the tCBT treatment arm with CWP and without CWP will be made at each of the three time points. Binary and nominal categorical variables will be compared with chi-squared tests. Continuous and discrete variables will be compared with independent t-tests or Mann-Whitney tests as appropriate.

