$\text{Logit}(p(\text{CWP})) = \text{constant} + \text{treatment effect} + \text{blocking effect} + \text{other covariate effects} + \text{random error}.$

The treatment effect will be a fixed effect. The blocking effect will comprise the number of high-risk factors present (fixed effect) and GP practice (random effect, n=16 practices).

The other covariates that will be considered in the model are: age and sex. The expectation is that these covariates will be balanced through randomisation, but they are both known to be related to the likelihood of the development of CWP. Multiple imputation (MI) analysis will be used to examine sensitivity to missing data.

After discussion at the TSC it was decided that it will not be possible to consider the therapist effect in a formal way between the two arms. Only one arm will be exposed to the therapists and even descriptive approach was disregarded as the number of participants was expected to vary widely between different therapists.

2.4.5.ANALYSIS OF SECONDARY OUTCOMES

Secondary outcomes

Comparisons with appropriate hypothesis tests will be used for the secondary outcomes, pain, illness behaviour, somatic symptom reporting, sleep problems, quality of life and wellbeing, psychological distress, patient global impression of change measure and fatigue. Appropriate adjustment will be made for the stratification factor. The baseline value of the relevant outcome variable will also be included as a covariate. Given the multiple secondary outcomes, the p-value used to denote statistical significance will reflect the multiple comparisons.

An appropriate adjustment will be made for the stratification factor as described above, the blocking effect will be addressed through including the number of high-risk factors present (fixed effect) and GP practice (random effect).

There are 8 secondary outcomes. The most conservative approach would be to use Bonferroni $p=0.05/8=0.00625$ or a family-wise error rate of $\alpha=0.0065$ (so $1-(1-\alpha)^8 = 0.05$). A less conservative approach would be to take $p=0.01$ for significance of the secondary outcomes and this was agreed as appropriate at the TSC meeting of 9 September 2016.

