Number of high-risk factors present: 3 vs 2			
Age			
Gender			
Random effect: GP practice			

Table 25-Table 30 similar for somatic symptoms, sleep problems, distress - General Health Questionnaire score, QoL from EQ5D score, QoL from ICECAP score, fatigue

Table 31: Secondary outcome adjusted analysis of Global impression of change measure score at 3, 12 and 24 months in multilevel model in the tCBT and usual care arms on the ITT population

	Multilevel at 3 time points		
	Adjusted coefficient	95% CI	p-value
Treatment: tCBT vs Usual care			
3 to 12 months			
12 to 24 months			
Number of high-risk factors present: 3 vs 2			
Age			
Gender			
Random effect: GP practice			

Note: Global impression of change measure score may not need to be adjusted for baseline.

Table 32: Responder analysis (tCBT treatment group)

	CWP at 12 months (n=)	No CWP at 12 months (n=)	p-value
Presence of pain n (%)			
Illness behaviour Score Median (IQR)			
Somatic symptom reporting			
Sleep problems Score Median (IQR)			
Gender n (%) Male Female			
Age n Mean (SD) Median (IQR)			
Health board n (%)			
Distress - General Health Questionnaire Median (IQR)			
QoL from EQ5D Median (IQR)			
QoL from ICECAP Median (IQR)			
Fatigue Median (IQR)			
Global impression of change measure Median (IQR)			
Completion of treatment n (%)			
Length of time between randomisation and treatment start Median (IQR)			

Table 33: Patient withdrawals

Reasons for withdrawal	tCBT (n=)	Usual Care (n=)	Total (n=)
Number who withdrew from the study (%)			
Primary reason for withdrawal ¹			

¹ Denominator is the number of patients that withdrew from the study.

Table 34: Distribution of withdrawals by baseline characteristics

	Withdrawals (n=)	Non-withdrawals (n=)
Gender n (%) Male Female	xx xx	xx xx
Age (n) Mean (SD) Median (IQR) (min, max)		
Presence of pain n (%)		
Illness behaviour Score > 4 n (%) Symptoms scale Score > 2 n (%) Sleep problems Score > 4 n (%)		
2 factors present n (%) 3 factors present n (%)		
GP practice n (%) Distress - General Health Questionnaire Median (IQR) QoL from EQ5D Median (IQR) QoL from ICECAP Median (IQR) Fatigue Median (IQR) Global impression of change measure Median (IQR)

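### The responder analysis looks only inside the tCBT arm, so it mixes prognosis with effect modification and cannot show who responds to tCBT

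*SAP*

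**What the plan says.** SAP 2.4.9 defines the contrast by outcome within one arm: tCBT participants without CWP at 12 months "will be compared with those in the treatment group who do have (CWP) in terms of other variables". It then extends this: "Simple comparisons between those within the tCBT treatment arm with CWP and without CWP will be made at each of the three time points".

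Twelve variables are listed: the symptom, illness behaviour and sleep scores, age, gender, health board, General Health Questionnaire distress, fatigue, EQ-5D, ICECAP, and finally "completion of treatment; and length of time between randomisation and treatment start". The tests are unadjusted: "Binary and nominal categorical variables will be compared with chi-squared tests", with t-tests or Mann-Whitney tests for the rest. The section does not say whether the scores are baseline or follow-up values.

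Table 32 has a CWP column, a no-CWP column and a p-value. It has no usual-care column. It also adds two rows that 2.4.9 does not list: presence of pain and global impression of change.

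Nothing elsewhere supplies a between-arm version. In SAP 2.4.4, "The treatment effect will be a fixed effect", alongside risk-factor count, age, sex and GP practice, with no interaction term. On age and sex the same section says "they are both known to be related to the likelihood of the development of CWP". Protocol 6.5 gives a relation to CWP onset as the reason for stratifying on the number of non-pain high-risk factors.

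**The concern.** Response to a preventive treatment means that the outcome differs because of the treatment. Someone in the tCBT arm without CWP may have been protected by tCBT, or may never have been going to develop it. The planned table cannot tell these apart, because it has no information on what happens to similar people under usual care.

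The listed variables make this more than theoretical. The documents call age and sex prognostic, and the three scores are the components of a count that they also call prognostic. Such variables could separate those with and without CWP even if tCBT did nothing. Under the title of responder analysis, the result could be read as showing which patients benefit, and could influence whom the intervention is later offered to.

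**Working it through.** **Inputs.** CWP 21% under usual care and 12% under tCBT, 90% power, 5% level, 80% questionnaire return, 473 per arm (SAP 1.4); two-sided testing (SAP 2.4.1). *Assumed, not in the documents:* a binary baseline factor with 50% prevalence, and an odds ratio (OR) for CWP of 1.5 to 3.

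**1. Number analysed.** The two-proportion formula with continuity correction gives 378 per arm, and 378/0.80 = 472.5, rounded up to 473. The plan's figure is reproduced, so 378 analysed in the tCBT arm is used below.

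**2. How many responders owe their status to tCBT?**
- Free of CWP on tCBT: 1 − 0.12 = 88%, or 0.88 × 378 ≈ 333 people.
- Free of CWP under usual care: 1 − 0.21 = 79%.
- The share free under both conditions is at most 79% (if tCBT never causes CWP) and at least 79 + 88 − 100 = 67%.
- As a share of responders: 67/88 = 76% up to 79/88 = 90%.

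**3. If tCBT has no effect.** CWP in the tCBT arm is then 21%. Split 378 into two groups of n = 189 with risks p0 and p1 that average 21%. With p̄ the mean of p0 and p1,

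power = Φ{ [ |p1 − p0| − 1.96·√(2p̄(1 − p̄)/n) ] / √( [p0(1 − p0) + p1(1 − p1)]/n ) }.

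| OR of the factor | p0, p1 | Power to flag it |
|---|---|---|
| 1.5 | 17.7%, 24.3% | 36% |
| 2 | 15.4%, 26.6% | 77% |
| 2.5 | 13.7%, 28.3% | 94% |
| 3 | 12.3%, 29.7% | 99% |

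A purely prognostic factor is often flagged although nobody responds to treatment. At 12% CWP the powers are 24%, 57%, 79% and 90%.

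**4. Two examples in which tCBT works overall (21% to 12%, factor OR 2 in usual care).** Usual-care risks are 15.4% without the factor and 26.6% with it.
- *Same treatment OR at both levels.* tCBT risks are 8.4% and 15.6%. The planned comparison has about 57% power to mark the factor as a sign of non-response. Yet the absolute reduction is 6.9 points without the factor and 11.1 points with it (unrounded risks), so the group that looks less responsive gains more in absolute terms. A both-arm interaction test on the odds scale rejects at its nominal 5%.
- *Ratio of treatment ORs 0.5.* tCBT risks are 12% at both levels, so the planned comparison shows nothing. The reductions are 3.4 and 14.6 points. With 189 per cell, the standard error of the log ratio is √Σ[1/(189·p(1 − p))] ≈ 0.41, and the interaction test has about 39% power.

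**5. Number of tests.** 12 variables × 3 times = 36. The 1% threshold in SAP 2.4.5 covers the secondary outcomes, so the 5% default in SAP 2.4.1 applies here: 36 × 0.05 = 1.8 expected false positives if all 36 are null. That is an upper limit, since age and sex are stated not to be null.

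**6. The two added rows.** The note to Table 13 says that all patients have pain at baseline, so presence of pain can vary only at follow-up, where anyone with CWP has pain by definition. Protocol 6.6 and SAP 2.4.6 describe global impression of change as an addition to the follow-up questionnaires, although Tables 6 and 21 carry a baseline row for it. Neither is a usable baseline predictor.

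**The case against.** The best defence is that the SAP claims little. It gives no purpose beyond the heading, calls the work simple comparisons, and labels the columns of Table 32 by CWP status within the tCBT group. A reader might infer that the plan will declare which patients benefit; the documents do not say so. The harm is a possible misreading, prompted mainly by the word responder.

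Other strong readings also go too far:
- That the analysis shows prognosis only. It mixes prognosis with any effect modification. Moreover, any score measured at follow-up would give a concurrent association, and the SAP leaves the timing open.
- That the number of risk factors will emerge as a predictor of response. The count is a stratification factor and model covariate; 2.4.9 and Table 32 list its three component scores instead.
- That 90% of responders were never at risk. That is the upper end of the range and needs the assumption that tCBT never causes CWP.

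It is also fair that completion of treatment has no usual-care counterpart, so it can only be examined within the tCBT arm, and that SAP 2.4.8 already tabulates it. Interaction tests would be weak and would themselves be numerous. These points limit the claim and shape the remedy. They do not supply the missing comparison with usual care.

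**Conclusion.** The point holds as a fault of method and labelling in a supplementary analysis. A tCBT-only comparison cannot identify who responds to tCBT, and it can mislead in both directions: it can flag a purely prognostic factor when there is no treatment effect, and it can miss real effect modification.

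The range of 76% to 90% rests only on the two planned rates. The power figures depend on the assumed prevalence and odds ratios and are illustrations, not forecasts. A reader might infer that the trial's main conclusion is at risk; it is not, because the primary estimate, its test and the sample size do not use this analysis.

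**What to change.** **Minimum change, SAP 2.4.9 and Table 32.**
- Retitle both as predictors of CWP in the tCBT arm.
- State that the scores are baseline values.
- Remove presence of pain and global impression of change.
- Show completion of treatment and time from randomisation to treatment start, both determined after randomisation, descriptively and without tests.

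**To address who benefits.** Use both arms. For each of the ten remaining variables (12 − 2), one at a time, add its treatment interaction to the 12-month primary model, with its main effect where that is not already present. Report the interaction estimate with its confidence interval, label the set exploratory, and state how many tests were done.

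**Cost.** A few extra model fits on data already collected, plus wording changes. The downside is low power (about 39% in the example with a ratio of odds ratios of 0.5), so many results may be inconclusive and should be reported as such.

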2.5. WITHDRAWALS

Participants will have the option to withdraw from the treatment or the study at any time. Those withdrawing from the treatment will continue to be sent follow-up questionnaires unless they specifically request not to receive them. Failure of any participant to complete a follow-up questionnaire at any particular time-point will not be counted as a withdrawal unless the participant requests not to receive any further follow-ups.

The number of participants withdrawing from the trial will be recorded within each randomised group. Details of reasons for withdrawal will be provided with the CONSORT diagram.

2.6. DATA STORAGE

Confidentiality: All evaluation forms, reports, and other records will be identified in a manner designed to maintain participant confidentiality. All records will be kept in a secure storage area with limited access.

Data Protection: All Investigators and study site staff involved with this study will comply with the requirements of the Data Protection Act 1998 with regard to the collection, storage, processing and disclosure of personal information and will uphold the Act's core principles. Computers used to collate the data will have limited access measures via user names and passwords. Published results will not contain any personal data that could allow identification of individual participants.

Study Record Retention: All study documentation will be kept for a minimum of 5 years from the protocol defined end of study point. When the minimum retention period has elapsed, study documentation will not be destroyed without permission from the sponsor.

End of Study: The end of study is defined as data collection at 2 years from the last participant's date of beginning treatment or dummy treatment start date.

3. DUMMY TABLES

A consort diagram for the trial will be produced.

The following dummy tables are examples of what the final tables are expected to look like, but the actual final format may change.

Table 1: Number of patients in the Intention to treat (ITT) and per protocol (PP) populations, overall and by treatment group

Population	tCBT	Usual care	Overall
ITT	xx	xx	xx
PP	xx	xx	xx

Table 2: Number randomised by practice

Practice	Randomised
1	xx
2	xx
3	xx
...	...
14	xx
Total	xx

Table 3: Number of patients in the Intention to treat (ITT) population by study practice and treatment group

Practice	tCBT	Usual care	Overall
1	xx	xx	xx
2			
...	xx	xx	xx
14	xx	xx	xx
Total	xx	xx	xx

Table 4: Number of patients in the per protocol (PP) population by study practice and treatment group

Practice	tCBT	Usual care	Overall
1	xx	xx	xx
2			
...	xx	xx	xx
14	xx	xx	xx
Total	xx	xx	xx

Table 5: Measures of treatment engagement in the tCBT arm

	tCBT
Initial session n (%)	
No	
Yes	
Number of weekly sessions attended n (%)	
0	
1	
2	
3	
4	
5	
6	
Booster session at 3 months n (%)	
No	
Yes	
Booster session at 6 months n (%)	
No	
Yes	
Treatment completed n (%)	
No	
Yes	

Table 6: Baseline characteristics by treatment arm in the ITT population

	tCBT (n=)	Usual care (n=)	Overall (n=)
Gender n (%)	xx	xx	Xx
Male			
Female	xx	xx	xx
Age (n)			
Mean (SD)			
Median (IQR)			
(min, max)			
Pain self-report n (%)			
Illness behaviour Score > 4 n (%)			
Symptoms scale Score > 2 n (%)			
Sleep problems Score > 4 n (%)			
2 factors present n (%)			
3 factors present n (%)			
GP practice n (%)			
Distress - General Health Questionnaire			
Median (IQR)			
QoL from EQ5D Median (IQR)			
QoL from ICECAP Median (IQR)			
Fatigue Median (IQR)			
Global impression of change measure			
Median (IQR)			

Table 7: Outcomes at the three time points 3 months, 12 months and 24 months by treatment arm in the ITT population

	tCBT (n=)	Usual care (n=)	Overall (n=)
CWP n (%)	xx	xx	xx
Presence of pain n (5)	xx	xx	xx
Illness behaviour Score Median (IQR)	xx	xx	xx
Somatic symptom reporting	xx	xx	xx
Sleep problems Score Median (IQR)	xx	xx	xx
Distress - General Health Questionnaire Median (IQR)	xx	xx	xx
QoL from EQ5D Median (IQR)	xx	xx	xx
QoL from ICECAP Median (IQR)	xx	xx	xx
Fatigue Median (IQR)	xx	xx	xx
Global impression of change measure Median (IQR)	xx	xx	xx

Note: Table repeated for outcomes at 12 months and 24 months by treatment arm

Table 8: Primary outcome 12 month unadjusted and adjusted analysis of presence of CWP in the tCBT and usual care arms on the ITT population

	Unadjusted OR	95% CI	p-value	Adjusted OR	95% CI	p-value
Treatment: tCBT vs Usual care						
Number of high-risk factors present: 3 vs 2						
Age						
Gender						
Random effect: GP practice						

Table 9: Primary outcome 12 month unadjusted and adjusted analysis of presence of CWP in the tCBT and usual care arms on the PP population (sensitivity analysis)

	Unadjusted OR	95% CI	p-value	Adjusted OR	95% CI	p-value
Treatment: tCBT vs Usual care						
Number of high-risk factors present: 3 vs 2						
Age						
Gender						
Random effect: GP practice						

Table 10: Primary outcome 12 month unadjusted and adjusted analysis of presence of CWP in the tCBT and usual care arms on the ITT population with multiple imputation (sensitivity analysis)

	Unadjusted OR	95% CI	p-value	Adjusted OR	95% CI	p-value
Treatment: tCBT vs Usual care						
Number of high-risk factors present: 3 vs 2						
Age						
Gender						
Random effect: GP practice						

Table 11: Primary outcome 3 and 24 month adjusted analysis of presence of CWP in the tCBT and usual care arms on the ITT population

	3 months			24 months		
	Adjusted OR	95% CI	p-value	Adjusted OR	95% CI	p-value
Treatment: tCBT vs Usual care						
Number of high-risk factors present: 3 vs 2						
Age						
Gender						
Random effect: GP practice						

Table 12: Primary outcome 3 and 24 month adjusted analysis of presence of CWP in the tCBT and usual care arms on the PP population

	3 months			24 months		
	Adjusted OR	95% CI	p-value	Adjusted OR	95% CI	p-value
Treatment: tCBT vs Usual care						
Number of high-risk factors present: 3 vs 2						
Age						
Gender						
Random effect: GP practice						

Note: This table will be repeated for 3 months and 24 months

Table 13: Secondary outcome adjusted analysis of presence of pain in the tCBT and usual care arms on the ITT population

	3 Months			12 Months			24 Months		
	Adjusted OR	95% CI	p-value	Adjusted OR	95% CI	p-value	Adjusted OR	95% CI	p-value
Treatment: tCBT vs Usual care									
Number of high-risk factors present: 3 vs 2									
Age									
Gender									
Random effect: GP practice									

Note: As all patients have pain at baseline there is no adjustment for this as there is for other secondary outcomes

Table 14: Secondary outcome adjusted analysis of illness behaviour score in the tCBT and usual care arms on the ITT population

	3 Months			12 Months			24 Months		
	Adjusted coefficient	95% CI	p-value	Adjusted coefficient	95% CI	p-value	Adjusted coefficient	95% CI	p-value
Treatment: tCBT vs Usual care									
Illness behaviour score at baseline									
Number of high-risk factors present: 3 vs 2									
Age									
Gender									
Random effect: GP practice									

Table 15: Secondary outcome adjusted analysis of somatic symptom score in the tCBT and usual care arms on the ITT population

	3 Months			12 Months			24 Months		
	Adjusted coefficient	95% CI	p-value	Adjusted coefficient	95% CI	p-value	Adjusted coefficient	95% CI	p-value
Treatment: tCBT vs Usual care									
Somatic symptom score at baseline									
Number of high-risk factors present: 3 vs 2									
Age									
Gender									
Random effect: GP practice									

Table 16: Secondary outcome adjusted analysis of sleep problems score in the tCBT and usual care arms on the ITT population

	3 Months			12 Months			24 Months		
	Adjusted coefficient	95% CI	p-value	Adjusted coefficient	95% CI	p-value	Adjusted coefficient	95% CI	p-value
Treatment: tCBT vs Usual care									
Sleep problems score at baseline									
Number of high-risk factors present: 3 vs 2									
Age									
Gender									
Random effect: GP practice									

Table 17: Secondary outcome adjusted analysis of Distress - General Health Questionnaire score in the tCBT and usual care arms on the ITT population

	3 Months			12 Months			24 Months		
	Adjusted coefficient	95% CI	p-value	Adjusted coefficient	95% CI	p-value	Adjusted coefficient	95% CI	p-value
Treatment: tCBT vs Usual care									
Distress - General Health Questionnaire score at baseline									
Number of high-risk factors present: 3 vs 2									
Age									
Gender									
Random effect: GP practice									

Table 18: Secondary outcome adjusted analysis of QoL from EQ5D score in the tCBT and usual care arms on the ITT population

	3 Months			12 Months			24 Months		
	Adjusted coefficient	95% CI	p-value	Adjusted coefficient	95% CI	p-value	Adjusted coefficient	95% CI	p-value
Treatment: tCBT vs Usual care									
QoL from EQ5D score at baseline									
Number of high-risk factors present: 3 vs 2									
Age									
Gender									
Random effect: GP practice									

Table 19: Secondary outcome adjusted analysis of QoL from ICECAP score in the tCBT and usual care arms on the ITT population

	3 Months			12 Months			24 Months		
	Adjusted coefficient	95% CI	p-value	Adjusted coefficient	95% CI	p-value	Adjusted coefficient	95% CI	p-value
Treatment: tCBT vs Usual care									
QoL from ICECAP score at baseline									
Number of high-risk factors present: 3 vs 2									
Age									
Gender									
Random effect: GP practice									

Table 20: Secondary outcome adjusted analysis of Fatigue score in the tCBT and usual care arms on the ITT population

	3 Months			12 Months			24 Months		
	Adjusted coefficient	95% CI	p-value	Adjusted coefficient	95% CI	p-value	Adjusted coefficient	95% CI	p-value
Treatment: tCBT vs Usual care									
Fatigue score at baseline									
Number of high-risk factors present: 3 vs 2									
Age									
Gender									
Random effect: GP practice									

Table 21: Secondary outcome adjusted analysis of Global impression of change measure score in the tCBT and usual care arms on the ITT population

	3 Months			12 Months			24 Months		
	Adjusted coefficient	95% CI	p-value	Adjusted coefficient	95% CI	p-value	Adjusted coefficient	95% CI	p-value
Treatment: tCBT vs Usual care									
Global impression of change measure score at baseline									
Number of high-risk factors present: 3 vs 2									
Age									
Gender									
Random effect: GP practice									

Table 22: Primary outcome presence of CWP at 3, 12 and 24 months in multilevel model in the tCBT and usual care arms on the ITT population

	Multilevel at 3 time points		
	Adjusted OR	95% CI	p-value
Treatment: tCBT vs Usual care			
3 to 12 months			
12 to 24 months			
Number of high-risk factors present: 3 vs 2			
Age			
Gender			
Random effect: GP practice			

Table 23: Secondary outcome presence of pain at 3, 12 and 24 months in multilevel model in the tCBT and usual care arms on the ITT population

	Multilevel at 3 time points		
	Adjusted OR	95% CI	p-value
Treatment: tCBT vs Usual care			
3 to 12 months			
12 to 24 months			
Number of high-risk factors present: 3 vs 2			
Age			
Gender			
Random effect: GP practice			

Table 24: Secondary outcome illness behaviour score at 3, 12 and 24 months in multilevel model in the tCBT and usual care arms on the ITT population

	Multilevel at 3 time points		
	Adjusted coefficient	95% CI	p-value
Treatment: tCBT vs Usual care			
3 to 12 months			
12 to 24 months			
Illness behaviour score at baseline			
Number of high-risk factors present: 3 vs 2			
Age			
Gender			
Random effect: GP practice			

Table 25-Table 30 similar for somatic symptoms, sleep problems, distress - General Health Questionnaire score, QoL from EQ5D score, QoL from ICECAP score, fatigue

Table 31: Secondary outcome adjusted analysis of Global impression of change measure score at 3, 12 and 24 months in multilevel model in the tCBT and usual care arms on the ITT population

	Multilevel at 3 time points		
	Adjusted coefficient	95% CI	p-value
Treatment: tCBT vs Usual care			
3 to 12 months			
12 to 24 months			
Number of high-risk factors present: 3 vs 2			
Age			
Gender			
Random effect: GP practice			

Note: Global impression of change measure score may not need to be adjusted for baseline.

Table 32: Responder analysis (tCBT treatment group)

	CWP at 12 months (n=)	No CWP at 12 months (n=)	p-value
Presence of pain n (%)			
Illness behaviour Score Median (IQR)			
Somatic symptom reporting			
Sleep problems Score Median (IQR)			
Gender n (%) Male Female			
Age n Mean (SD) Median (IQR)			
Health board n (%)			
Distress - General Health Questionnaire Median (IQR)			
QoL from EQ5D Median (IQR)			
QoL from ICECAP Median (IQR)			
Fatigue Median (IQR)			
Global impression of change measure Median (IQR)			
Completion of treatment n (%)			
Length of time between randomisation and treatment start Median (IQR)			

Table 33: Patient withdrawals

Reasons for withdrawal	tCBT (n=)	Usual Care (n=)	Total (n=)
Number who withdrew from the study (%)			
Primary reason for withdrawal ¹			

¹ Denominator is the number of patients that withdrew from the study.

Table 34: Distribution of withdrawals by baseline characteristics

	Withdrawals (n=)	Non-withdrawals (n=)
Gender n (%) Male Female	xx xx	xx xx
Age (n) Mean (SD) Median (IQR) (min, max)		
Presence of pain n (%)		
Illness behaviour Score > 4 n (%) Symptoms scale Score > 2 n (%) Sleep problems Score > 4 n (%)		
2 factors present n (%) 3 factors present n (%)		
GP practice n (%) Distress - General Health Questionnaire Median (IQR) QoL from EQ5D Median (IQR) QoL from ICECAP Median (IQR) Fatigue Median (IQR) Global impression of change measure Median (IQR)
